### 3. LIST OF ABBREVIATIONS AND DEFINITIONS OF TERMS

RTA	Recombinant tuberculosis allergen
BCG	Bacillus Calmette-Guérin
WHO	World Health Organization
CI	Confidence interval
CRF	Case report form
IFN- $\gamma$	Interferon-gamma
LEC	Local Ethics Committee
First Volunteer In	First visit of the first Volunteer
RTA test	Test with recombinant tuberculosis allergen
AE	Adverse event
AR	Adverse reaction
Last Volunteer Out	Last visit of the last Volunteer
SUSAR	Suspected unexpected serious adverse (drug) reaction
Suspected Adverse Reaction	A form of the Council of International Organizations of Medical Sciences Reporting Form
Specificity	Probability to get a negative test result in a subject without the disease
Sensitivity	Probability to get a positive test result in a subject with the disease
The NMRC TPID	National Medical Research Center of Tuberculosis, Pulmonology, and Infectious Diseases, a federal state-financed institution of the Ministry of Health of the Russian Federation
CFP-10	Recombinant culture filtrate protein 10 kDa
ESAT-6	Recombinant early secreted antigenic target 6 kDa
GCP	Good Clinical Practice
GMP	Good Manufacturing Practice
ICH-GCP	The International Conference on Harmonisation of Good Clinical Practice
MTb	Mycobacterium tuberculosis
T-SPOT®.TB	Diagnostic assay with a reagent kit for in vitro diagnosis of tuberculosis infection T-SPOT.TB, Oxford Immunotec Ltd., United Kingdom

## 6. INTRODUCTION

Tuberculosis remains the most common infection, affecting more than 10 million people annually and causing an estimated 1.2 million deaths [WHO, Global Tuberculosis report 2020]. For a century, tuberculin has been used worldwide to diagnose tuberculosis and detect latent tuberculosis infection [von Pirquet C., 1907, Mantoux M., 1912]. The major disadvantage of the tuberculin test is a high rate of false positive reactions due to cross-reactivity with PPD antigens that are present in many mycobacteria and strains of *Bacillus Calmette-Guérin* (BCG). In a meta-analysis of 14 studies from other countries, the pooled sensitivity of the tuberculin test was 71% [1]. In a large review of foreign literature and meta-analysis, Rangaka et al. (2012) indicate that a positive tuberculin reaction has a low prognostic value in assessing the probability of the disease [2].

The limited specificity of the tuberculin skin test is particularly relevant in large-scale BCG vaccination programs and in the screening a large population of tuberculosis-infected patients, i.e. in most countries with high tuberculosis rates. The discovery of *Mycobacterium* tuberculosis-specific antigens that are absent in *Mycobacterium bovis* BCG and most mycobacteria resulted in the development of *in vitro* tests measuring gamma interferon (INF- $\gamma$ ) production (Interferon-Gamma Release Assays or IGRA) in response to stimulation with these antigens. The genome of *Mycobacterium bovis* BCG and most non-tuberculous mycobacteria has no region of difference (RDI) containing genes encoding these proteins. These tests showed high sensitivity and almost absolute specificity.

In 2009, the diagnostic product recombinant tuberculosis allergen (RTA), a recombinant protein CFP10-ESAT6 produced by *Escherichia coli* BL21(DE3)/pCFP-ESAT, was granted marketing authorization in Russia. The Russian skin test with RTA is analogous to the IGRA-based tests. No special laboratory equipment is required to perform the skin test. The RTA test showed high sensitivity (over 95%) in the mass screening of patients in Moscow in 2012–2014 [3,4], as well as in Novosibirsk Oblast [5], Ryazan Oblast [6], and St. Petersburg [7].

The following normative documentation regulates the use of the RTA test in Russia: Order of the Ministry of Health of the Russian Federation No. 855 of October 29, 2009; Order of the Ministry of Health of the Russian Federation No. 951 of December 29, 2014; Order of the Ministry of Health of the Russian Federation No. 124H of March 21, 2017; the clinical guidelines “Latent tuberculosis infection in children,” “Tuberculosis in children” (Moscow, 2020) [10], and the clinical guidelines “Tuberculosis in adults” (Moscow, 2020) [11].

RTA has been used in the Russian Federation and CIS since 2009. More than 60 million tests have been performed since its authorization. In 2015, per Order of the Ministry of Health of Russia No. 951 of December 29, 2014, the RTA test replaced the Mantoux test in the screening of tuberculosis in children 8 years of age or older.

Studies have shown a significant increase in tuberculosis rates (37-fold in schoolchildren aged 8–17 years compared with the Mantoux test [12]) in primary healthcare centers following the transition to the screening using RTA.

The specificity of the RTA test was also evaluated in a local (Moscow) patient population with a low tuberculosis rate and a low risk of tuberculosis infection (contacts of pregnant women). In 2015–2016, 7,249 tests were performed in this population which most closely mirrors the permanent population of Moscow. A positive or equivocal RTA test result was found in 0.3%

(95% confidence interval [CI] 0.2–0.6%) and 1.0% (95% CI 0.7–1.4%) of evaluated pregnant contacts ( $p < 0.05$ ) in 2015 and 2016, respectively. No tuberculosis patients were identified in this population. Thus, the specificity of the test was 99.0–99.7% [13].

With decreasing incidence of tuberculosis in the Russian Federation, it seems relevant to confirm the specificity of the RTA test in a population of healthy subjects who are not at risk of tuberculosis (with a negative T-SPOT.TB assay result) in real clinical practice in the subjects of the Russian Federation with low rates of tuberculosis incidence and mortality.

It should be noted that specificity, which is one of the key characteristics of a diagnostic test, is defined as the ability of a test to correctly identify subjects without the disease.

## 7. STUDY OBJECTIVES

### 7.1 Primary objective

To evaluate the specificity of the test with recombinant tuberculosis allergen (RTA) following intradermal administration in healthy subjects 18 to 30 years of age, not belonging to the risk group for the development of tuberculosis in the regions of the Russian Federation with a favorable epidemiological situation for tuberculosis.

The specificity of the RTA test is defined as the relative frequency of subjects in a healthy population (individuals with no signs of tuberculosis infection) who have a negative test reaction (no infiltration/papule) at the injection site).

### 7.2 Secondary objectives

To record all adverse events that occurred within 28 days after the test

### 7.3 Primary endpoint

- Absolute number and percentage of the volunteers with negative and positive test results with RTA (individuals with no signs of tuberculosis infection) based on the results of the assessment (measurement) of the infiltrate 72 hours after the test.

### 7.4 Secondary endpoints

- Local (at the injection site) adverse events (itching, swelling, soreness, pain) within 72 hours after administration of RTA.
- General and local adverse reactions within 28 days after administration of RTA.

### 7.5 Primary variables:

Diameter of the infiltrate (papule) at the injection site, measured across the longitudinal axis of the forearm 72 hours after the intradermal test.

[figure not shown]
### 7.6 Secondary variables:

- Adverse events at the injection site within 28 days after the test
- All adverse events that occurred within 28 days after the test

## 8. STUDY DESIGN

### 8.1 Design

This clinical study is a prospective, multicenter, open-label study with the formation of a cohort of healthy adults (18-30 years of age) (not classified as at risk of tuberculosis, with no clinical symptoms of the disease, with a negative T-SPOT.TB test results) to evaluate the specificity of the test with recombinant tuberculosis allergen following administration of the investigational diagnostic product to each participant at a dose of 0.2 µg/0.1 mL. Study design is presented below (picture 1).

*Picture 1. Study design*

In this study, in accordance with the current national standards for diagnosis of tuberculosis in Russia, volunteers will undergo a comprehensive examination with an assessment of clinical manifestations of the disease (general and respiratory complaints) and an assessment of the objective status. Blood sampling for the T-SPOT.TB test will be performed before the test with recombinant tuberculosis allergen.

Volunteers' complaints, as well as adverse events that occurred during the follow-up period, will be recorded at all visits.

The main goal of this study is to evaluate the specificity of the skin test with recombinant tuberculosis allergen, defined as the relative frequency of participants in a population of healthy volunteers (with no signs of tuberculosis infection) whose test results are comparable to that of the T-SPOT.TB reference test.

**Visit 0** *Screening visit* is for an initial examination, in accordance with generally accepted principles of diagnosis and monitoring, which includes:

- obtaining the informed consent
- assignment of an individual volunteer number
- completion of the questionnaire on inclusion/non-inclusion criteria
- collection of the volunteer's medical history, allergic history, complaints
- collection of information on the inclusion/non-inclusion criteria
- physical examination, including measurement of height and weight
- measurement of heart rate, breath rate, blood pressure
- blood sampling for the T-SPOT.TB test.

**Visit 1** *A skin test injection visit (0-3 days post-screening) includes:*

- intradermal test with recombinant tuberculosis allergen in accordance with the regulatory documents in force in the Russian Federation in case of negative T-SPOT.TB test
- assessment of adverse events that occurred after the injection of the recombinant tuberculosis allergen.

**Visit 2** *An assessment visit (after 72 hours) includes:*

- assessment of the reaction to the intradermal test with recombinant tuberculosis allergen.
- assessment of adverse events that occurred after the injection of the recombinant tuberculosis allergen.

**Visit 3** *Follow-up Visit (28 days after Visit 1):*

- assessment of adverse events that occurred after the injection of the recombinant tuberculosis allergen.

The volunteer can enter screening and participate in the study only after signing the informed consent. After signing the informed consent the volunteer's compliance with the inclusion / non-inclusion criteria is assessed. If a volunteer meets at least one non-inclusion criterion, he/she will not be able to continue his/her participation in the study.

The T-SPOT.TB test will be performed at Visit 0 prior to the test with recombinant tuberculosis allergen as a reference method for diagnosis of tuberculosis infection.

If the result of the T-SPOT.TB test is negative and other inclusion criteria are met, the volunteer will be enrolled in the study and can continue his/her participation in the study (the study design is presented in Appendix 3).

For practical reasons, Visit 1 (product administration) should be scheduled for Monday, Tuesday, or Friday (to allow 72 hours follow-up after RTA administration). See section 9.3 for more information about visits.

The occurrence of an infiltrate of any size at the RTA injection site will be regarded as a positive result.

The T-SPOT.TB test results will be regarded as negative, indeterminate, or positive upon receiving results from the laboratory performing the test in accordance with the Instructions for use. If the result of the T-SPOT.TB test is indeterminate or positive, the volunteer will be excluded from further participation in the study.

All results will be recorded in the individual Case Report Form (CRFs) of the study participants.

Healthcare professionals will ensure that informed consent is obtained from the volunteers for the skin test and blood collection for research purposes.

Each volunteer participating in the study will be monitored throughout the study. Anonymized CRFs will be shared between the study sites by courier delivery or their copies via e-mail.

A CRF for each visit is provided in Appendix 4.

## **8.2 Study population and clinical study conduct**

Healthy individuals 18 to 30 years of age, not belonging to the risk group for the development of tuberculosis in the regions of the Russian Federation with a favorable epidemiological situation for tuberculosis.

## **8.3 Number of study subjects**

150 healthy BCG-vaccinated male and female volunteers 18 to 30 years of age.

## **8.4 Subject recruitment**

Volunteers will be recruited by the centers included in the study. They will comply with all inclusion criteria. Recruitment will be performed via announcements.

## **8.5 Inclusion criteria**

1. Signed informed consent for the participation in the study, as well as for the Investigator's access to medical records.
2. Age 18 to 30 years
3. A history of BCG vaccination (confirmed by medical documentation and/or the presence of BCG scar)
4. Healthy individual according to physical examination and medical records at screening.
5. Willingness to cooperate and follow the recommendations of the Investigator in accordance with the Protocol.

## **8.6 Non-inclusion criteria**

Subjects will not be enrolled in the study for any of the following reasons:

1. A history of tuberculosis or close contact with a patient with active tuberculosis for 5 years prior to the enrollment in the study.
2. Positive T-SPOT.TB test at the enrollment in the study
3. Treatment with drugs affecting immune system within 3 months prior to the enrollment in the study
4. Vaccination against any infections <1.5 months prior to the enrollment in the study
5. Vaccination with BCG <6 months prior to the enrollment in the study.
6. The Mantoux test with 2 TU and/or the test with the recombinant tuberculosis allergen was performed less than 6 months prior to the enrollment in the study.
7. Congenital or acquired immunodeficiency.
8. Active disease of the immune system
9. HIV infection.
10. The current condition of the skin interferes with the conduct and reading of skin tests (trauma, skin diseases).
11. A disease in which blood sampling poses a risk to the volunteer (hemophilia, other bleeding disorders) or obstructed venous access.
12. The volunteer currently participates in another clinical study or has participated in another clinical study within 3 months prior to the enrollment in the study.
13. Previous participation in clinical studies of ESAT-6 and/or CFP-10 antigens.
14. Pregnancy, lactation, pregnancy planning.
15. The reluctance of a female person to use effective barrier (including spermicidal gel), hormonal or intrauterine contraceptives during the study.
16. History of alcohol, drug, benzodiazepine, or other substance abuse within the 12 months prior to the enrollment in the study.
17. Use of alcoholic beverages within 24 hours prior to the visit.
18. A condition or disease that, in the opinion of the Investigator, is inappropriate for participation in the study.

## **8.7 Exclusion criteria**

1. Refusal to participate in the study.

## **8.8 Anticipated reasons for study discontinuation**

Volunteers may discontinue participation in the study at any time without giving a reason.

No medical events are foreseen that might cause a volunteer to drop out of the study, since invasive procedures are only performed during Visit 0 and Visit 1. Procedures performed at subsequent visits do not expose the study participant to any risk..

The study may be stopped at any time if the Principal Investigator concludes that participation in the study exposes the volunteers to unacceptable risks.

If for any reason a volunteer wishes to withdraw from the study or has to be withdrawn from the study at the discretion of the Principal Investigator, the date and reason for the withdrawal should be documented in the CRF.

### **8.8.1 Permanent contraindications**

Permanent contraindications are listed as the non-inclusion criteria in Section 8.6.

### **8.8.2 Temporary contraindications**

The Responsible Investigator may, at his or her discretion, decide to postpone a visit based on the health assessment findings of a subject on the scheduled testing day.

## 9. INVESTIGATIONAL MEDICINAL PRODUCT

Investigational medicinal product:

Generic name: Standard dilution of recombinant tuberculosis allergen

Trade name: Diaskintest

Manufacturer: GENERIUM JSC, Russian Federation

Dosage form: solution for intradermal injection.

Appearance: clear, colorless liquid

One dose of the product is 0.1 mL/0.2 µg

ATC code: V01AA20

### 9.1 Composition

**Investigational medicinal product:** Recombinant tuberculosis allergen (Diaskintest).

Recombinant protein CFP10-ESAT6 .....	0.2 µg
Sodium phosphate dibasic dihydrate .....	0.3876 mg
Sodium chloride .....	0.46 mg
Potassium phosphate monobasic.....	0.063 mg
Polysorbate 80 .....	0.005 mg
Phenol .....	0.25 mg
Water for injection .....	q.s. to 0.1 mL

### 9.2 Procedure

The RTA intradermal test is performed according to the current prescribing information for the medicinal product. An RTA dose of 0.1 mL is injected into the inner surface on the mid-third of the right or left forearm. The injection is performed using a 1-mL syringe with a short beveled needle (a tuberculin syringe).

A qualified healthcare professional will read the result of the skin test (diameter of hyperemia/infiltrate (papule) in mm) 72 hours after the RTA injection. An infiltrate (papule) of any size will be considered a positive result.

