#### 9.3.1 Assessment of specificity

Specificity is a key characteristic of a diagnostic assay, referring to its ability to correctly identify individuals without the disease.

The specificity of the RTA test is defined as the proportion of subjects who tested negative (no infiltration (papule) in the injection site) in a healthy population (i.e. without MTb exposure).

$$\text{Specificity} = \frac{\text{True negatives}}{\text{True negatives} + \text{False positives}}$$

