### 12.4 Statistical methods

The study involves the analysis of anonymized CRF data that will be performed using an MS Excel spreadsheet:

- Study subject number;
- Enrollment date;
- Sex;
- Date of birth;
- BCG vaccination status (presence of a scar);
- Height;
- Body weight;
- Complaints;
- Body temperature;
- RR per minute;
- HR;
- BP (mmHg);

- Lung auscultation: rhonchi or crackles;
- The RTA test result (mm);
- The T-SPOT.TB assay result.

Generally accepted statistical methods will be employed to analyze the study data using Microsoft® Excel® 2016 MSO application software package (version 2109 16.0.14430.20154, 32-bit, product code: 00333-59091-97459-AA884). The use of the software is planned for statistical analysis. Two-sided statistical tests at a statistical significance level of  $p < 0.05$  will be used.

Demographic and other baseline characteristics will be presented for all patients enrolled in the study (the full analysis set population).

The Shapiro-Wilk criterion will be used to determine the normality of the distribution. Parameters that are quantitative variables (including age) will be expressed as:

- Arithmetic mean (mean);
- 95% CI for the mean;

Qualitative and categorical variables (gender, etc.) will be expressed in absolute values (n/N) and proportions (%).

The study will evaluate the specificity of the RTA test (see. Paragraph 9.3.1).

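### Does reading hyperemia together with infiltrate, and listing one millimetre value for analysis, put the RTA specificity estimate at risk?

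*Combined protocol and SAP*

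**What the plan says.** The reading is described in Section 9.2: a qualified professional "will read the result of the skin test (diameter of hyperemia/infiltrate (papule) in mm) 72 hours after the RTA injection". The next sentence gives the rule: "An infiltrate (papule) of any size will be considered a positive result". Section 8.1 gives the same rule: "The occurrence of an infiltrate of any size at the RTA injection site will be regarded as a positive result".

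The primary endpoint in Section 7.3 is "Absolute number and percentage of the volunteers with negative and positive test results with RTA", based on measurement of the infiltrate at 72 hours. The primary variable in Section 7.5 is "Diameter of the infiltrate (papule) at the injection site". Section 9.3.1 defines specificity as the "proportion of subjects who tested negative (no infiltration (papule) in the injection site) in a healthy population", and Section 7.1 defines a negative reaction in the same way.

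Among the items to be analysed, Section 12.4 lists "The RTA test result (mm", with no separate entry for hyperemia and none for a positive or negative call. Section 8.1 places the case report form in Appendix 4, which is not part of the public text.

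The Introduction (Section 6) reports an earlier Moscow series: "A positive or equivocal RTA test result was found in 0.3" percent in 2015 and 1.0% in 2016. It concludes that specificity was 99.0–99.7%.

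**The concern.** Two things look wrong.

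The first is recording. The reader looks at hyperemia and infiltrate together, while the analysis list has one unlabelled millimetre value. If a redness-only diameter were entered there, and the analyst treated every value above zero as positive, a true negative would be counted as a false positive. The listed field alone would not reveal the error.

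The second is comparability. The Introduction's figure counts equivocal results against specificity, whereas this study has only negative and positive. If equivocal meant redness without infiltrate, the same reactions would give a higher specificity here than under the Introduction's rule, and a reader setting the two figures side by side could be misled.

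The stake is real because few non-negative results are expected. At the Introduction's rates, one or two wrongly coded readings would be as many as all the non-negative results expected in 150 volunteers.

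**Working it through.** **Inputs.** N = 150 (Section 8.3); planning specificity 0.9 (Section 12.5); background rate of positive or equivocal results 0.3% and 1.0% (Section 6). The documents give no rate of hyperemia without infiltrate, so a range of 0.5% to 5% is assumed below.

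**The plan's own precision figures.** With variance u(1−u)/N:
- u = 0.5: 0.25/150 = 0.00167, square root 0.0408. The plan gives 0.0017 and 0.041.
- u = 0.9: √(0.9 × 0.1/150) = 0.0245. The plan gives 0.024.

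The figures reproduce, and how hyperemia is recorded does not enter them.

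**What the rule says about a redness-only reaction.**
- Sections 7.1 and 9.3.1: negative means no infiltrate.
- Section 7.3: the endpoint is based on measuring the infiltrate.
- Section 7.5: the primary variable is the infiltrate diameter.
- Sections 8.1 and 9.2: positive means an infiltrate of any size.

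Hyperemia without infiltrate is negative under every one of these. Only the description of the reading in Section 9.2 mentions hyperemia, and the sentence after it restores the infiltrate rule. The list in Section 12.4 is a summary of data items: it also shows blood pressure as one entry. Read with Section 7.5, the millimetre value is most naturally the infiltrate diameter.

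**Size if the rule were broken.** Each miscoded reading costs 1/150 = 0.67 points. Starting from no positives, with exact (Clopper-Pearson) 95% intervals:

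| Miscoded | Specificity | 95% CI |
|---|---|---|
| 0 | 100% | 97.6–100% |
| 1 | 99.3% | 96.3–99.98% |
| 3 | 98.0% | 94.3–99.6% |
| 5 | 96.7% | 92.4–98.9% |

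In general, observed specificity = 1 − q − h·m, where q is the infiltrate rate, h the hyperemia-only rate and m the share of those coded positive. With q = 1.0% and every such reading miscoded (m = 1), h = 0.5%, 1%, 2% and 5% give 98.5%, 98.0%, 97.0% and 94.0%. Under the plan's rule m = 0, and the result is 99.0% whatever h is.

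**Expected count at the background rates.** 150 × 0.003 = 0.45 and 150 × 0.010 = 1.5 non-negative results. Three redness-only reactions in 150 would be a 2% rate, which is 2/1.0 = 2 to 2/0.3 ≈ 7 times the entire positive-or-equivocal rate in the background series.

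**Comparability.** 100 − 0.3 = 99.7 and 100 − 1.0 = 99.0, so equivocal results were indeed counted as non-negative. Rescoring all of them as negative could raise the background figure to 100% at most, so the definitional gap is at most 0.3 to 1.0 points. The sampling SD at N = 150 is √(0.997 × 0.003/150) = 0.45 points and √(0.99 × 0.01/150) = 0.81 points at those two specificities, and 2.4 points at the planning value. Even with no positives, the exact interval reaches down 2.4 points. If some equivocal results involved an infiltrate, they would be positive here too and the gap would shrink.

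**The case for a change.** The best case for a change is that it is almost free and makes the primary result checkable. The Section 12.4 list has no positive/negative item, so as listed the call has to be derived from the millimetre value. The local events named in Section 7.4 do not include redness, and Section 13.9 treats entries made directly in the case report form as source data, so an ambiguous entry may have no earlier record behind it. The study is open-label and everyone tested is T-SPOT.TB-negative, so readers know the expected answer. With 0.45 to 1.5 non-negative results expected at the background rates, one ambiguous reading matters.

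Much of this stands as a reason for tidy recording. The wording of Section 9.2 is loose, and no available text says where a redness-only diameter is entered. It does not show that the plan would misclassify anyone. The form in Appendix 4 may already separate the two measurements, and an analyst who meets an unlabelled millimetre value has the primary variable in Section 7.5 to say what it must be. Separate fields would be used with the same positivity rule, so the intended primary estimate would not change.

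The comparability argument is weaker. The primary objective is to evaluate specificity. The Introduction does speak of confirming it, but in a T-SPOT.TB-negative population in regions with low tuberculosis rates. No comparison with 99.0–99.7% is planned, and the sample size rests on 0.9. The background series was contacts of pregnant women in Moscow, with no T-SPOT.TB selection described, so the populations differ however redness is scored. The documents never define equivocal. Taking it to mean redness without infiltrate is a guess, and a sensitivity analysis built on that guess would not reliably recreate the earlier rule.

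**Conclusion.** No change to the plan is needed. The outcome is infiltrate alone wherever the protocol defines the endpoint, the primary variable, a negative or a positive. What is missing is a label on one data item, a gap that an analyst reading Section 7.5 fills correctly. Sample size, planned precision and the positivity rule are unaffected.

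The possible error is 0.67 points of specificity per reading coded against the rule. That is not trivial beside 0.45 to 1.5 expected non-negative results, but it is a conditional risk that the documents do not show to be present. The definitional difference from the Introduction's figure is at most 0.3 to 1.0 points, and no planned analysis depends on it.

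This conclusion assumes that the millimetre value in Section 12.4 is the infiltrate diameter, as Section 7.5 implies, and that the case report form does not contradict this. If the form had a single box in which a redness diameter could be entered as the test result, the recording question would need to be reopened. Anyone quoting the result beside 99.0–99.7% should mention that the earlier figure counted undefined equivocal results as non-negative. That belongs in the report and does not need a change to the plan.
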